9.2.7 Potential Drug Induced Liver Injury (DILI)

Wherever possible, timely confirmation of initial liver-related laboratory abnormalities should occur prior to the reporting of a potential DILI event. All occurrences of potential DILIs, meeting the defined criteria, must be reported as SAEs (see [Section 9.2](#) and [Appendix 3](#) for reporting details).

Potential drug induced liver injury is defined as:

- 1) AT (ALT or AST) elevation > 3 times upper limit of normal (ULN)

AND

- 2) Total bilirubin > 2 times ULN, without initial findings of cholestasis (elevated serum alkaline phosphatase),

AND

- 3) No other immediately apparent possible causes of AT elevation and hyperbilirubinemia, including, but not limited to, viral hepatitis, pre-existing chronic or acute liver disease, or the administration of other drug(s) known to be hepatotoxic.

9.2.8 Other Safety Considerations

Any significant worsening noted during interim or final physical examinations, electrocardiogram, x-ray filming, any other potential safety assessment required or not required by protocol should also be recorded as a nonserious or serious AE, as appropriate, and reported accordingly.

9.3 Overdose

For this study, any dose of abatacept greater than the protocol-required amount will be considered an overdose.

All occurrences of overdose must be reported as an SAE (see [Section 9.2](#)).

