9.2 Adverse Events

The definitions of an AE or serious adverse event (SAE) can be found in [Appendix 3](#).

AEs will be reported by the participant (or, when appropriate, by a caregiver, surrogate, or the participant's legally authorized representative).

The investigator and any designees are responsible for detecting, documenting, and reporting events that meet the definition of an AE or SAE and remain responsible for following up AEs that are serious, considered related to the study treatment or the study, or that caused the participant to discontinue before completing the study.

Contacts for SAE reporting specified in Appendix 3.

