An AE can therefore be any unfavorable and unintended sign (such as an abnormal laboratory finding), symptom, or disease temporally associated with the use of study treatment, whether or not considered related to the study treatment.
Events Meeting the AE Definition

• Any abnormal laboratory test results (hematology, clinical chemistry, or urinalysis) or results from other safety assessments (eg, ECG, radiological scans, vital signs measurements), including those that worsen from baseline, considered clinically significant in the medical and scientific judgment of the investigator. Note that abnormal lab tests or other safety assessments should only be reported as AEs if the final diagnosis is not available. Once the final diagnosis is known, the reported term should be updated to be the diagnosis.• Exacerbation of a chronic or intermittent pre-existing condition including either an increase in frequency and/or intensity of the condition.• New conditions detected or diagnosed after study intervention administration even though it may have been present before the start of the study.• Signs, symptoms, or the clinical sequelae of a suspected drug-drug interaction.• Signs, symptoms, or the clinical sequelae of a suspected overdose of either study intervention or a concomitant medication. Overdose, as a verbatim term (as reported by the investigator), should not be reported as an AE/SAE unless it is an intentional overdose taken with possible suicidal/self-harming intent. Such overdoses should be reported regardless of sequelae and should specify "intentional overdose" as the verbatim term
Events NOT Meeting the AE Definition

• Medical or surgical procedure (eg, endoscopy, appendectomy): the condition that leads to the procedure is the AE.• Situations in which an untoward medical occurrence did not occur (social and/or convenience admission to a hospital).

DEFINITION OF SAE

If an event is not an AE per definition above, then it cannot be an SAE even if serious conditions are met.

SERIOUS ADVERSE EVENTS

Serious Adverse Event (SAE) is defined as any untoward medical occurrence that, at any dose:

Results in death

Is life-threatening (defined as an event in which the participant was at risk of death at the time of the event; it does not refer to an event which hypothetically might have caused death if it were more severe)

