
Requires inpatient hospitalization or causes prolongation of existing hospitalization (see NOTE below)
 
NOTE:
 
The following hospitalizations are not considered SAEs in BMS clinical studies:
 
 • a visit to the emergency room or other hospital department < 24 hours, that does not result in admission (unless considered an important medical or life-threatening event) • elective surgery, planned prior to signing consent • admissions as per protocol for a planned medical/surgical procedure • routine health assessment requiring admission for baseline/trending of health status (e.g., routine colonoscopy) • medical/surgical admission other than to remedy ill health and planned prior to entry into the study. Appropriate documentation is required in these cases • admission encountered for another life circumstance that carries no bearing on health status and requires no medical/surgical intervention (e.g., lack of housing, economic inadequacy, caregiver respite, family circumstances, administrative reason) • admission for administration of anticancer therapy in the absence of any other SAEs (applies to oncology protocols)

Results in persistent or significant disability/incapacity

Is a congenital anomaly/birth defect

Is an important medical event (defined as a medical event(s) that may not be immediately life-threatening or result in death or hospitalization but, based upon appropriate medical and scientific judgment, may jeopardize the participant or may require intervention [e.g., medical, surgical] to prevent one of the other serious outcomes listed in the definition above.) Examples of such events include, but are not limited to, intensive treatment in an emergency room or at home for allergic bronchospasm; blood dyscrasias or convulsions that do not result in hospitalization.) Potential drug induced liver injury (DILI) is also considered an important medical event. (See Section 9.2.7 for the definition of potential DILI.)

Pregnancy and potential drug induced liver injury (DILI) must follow the same transmission timing and processes to BMS as used for SAEs (see [section 9.2.5](#) for reporting pregnancies).

Any component of a study endpoint that is considered related to study therapy should be reported as SAE (e.g., death is an endpoint, if death occurred due to anaphylaxis, anaphylaxis must be reported).

EVALUATING AES AND SAES

Assessment of Causality

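### Protocol Section 9.3 makes every abatacept overdose an SAE, while Appendix 3 excludes one without self-harm intent and without serious sequelae: an internal inconsistency in safety reporting

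*Protocol*

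**What the plan says.** Section 9.3 of the protocol defines overdose without any threshold, intent or symptom condition: "any dose of abatacept greater than the protocol-required amount will be considered an overdose". It then gives the reporting rule: "All occurrences of overdose must be reported as an SAE". For detail it refers the reader to Section 9.2, which says: "The definitions of an AE or serious adverse event (SAE) can be found in" Appendix 3.

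Appendix 3 takes a different line, under the events that meet the AE definition. What counts as an AE is: "Signs, symptoms, or the clinical sequelae of a suspected overdose of either study intervention or a concomitant medication". The overdose itself is handled separately: "Overdose, as a verbatim term (as reported by the investigator), should not be reported as an AE/SAE unless it is an intentional overdose". The full clause shows how narrow the exception is: "unless it is an intentional overdose taken with possible suicidal/self-harming intent". Overdoses of that kind are to be reported whether or not sequelae follow. Appendix 3 then closes the route from non-AE to SAE: "If an event is not an AE per definition above, then it cannot be an SAE even if serious conditions are met".

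Both texts are current. Nothing in the visible protocol says which of them prevails.

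**The concern.** An investigator who follows Section 9.3 to its cited source arrives at a definition that contradicts it. For an accidental, symptom-free overage there is no sign or symptom to name, so the only term available for an SAE report is overdose, which Appendix 3 says not to use. The site cannot obey both instructions, and Section 9 of the protocol allows no waivers.

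At stake is whether an overage produces an SAE record. That decides three things: whether the 24-hour report to the sponsor is due (Section 9.2.1 and Appendix 3), whether the event enters the SAE listing (SAP Section 6.6.2), and whether it is counted among the tabulated AEs (SAP Section 6.6.3). Two sites with identical events could report them differently, and both could cite the protocol.

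**Working it through.** No sample size, power or error rate is involved, and the plan states no figure to reproduce. The check is to apply each rule to every combination of intent (self-harm or not) and sequelae (none, non-serious, serious).

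**Inputs**
- Section 9.3: every abatacept dose above the required 750 mg is an overdose, and every overdose is reported as an SAE.
- Appendix 3, overdose as a term: reportable only with possible self-harm intent, and then regardless of sequelae.
- Appendix 3, sequelae: these are the AE, and they are serious only if they meet an SAE criterion.
- Appendix 3, gate: what is not an AE cannot be an SAE.

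| Self-harm intent | Sequelae | Section 9.3 | Appendix 3 | Is an SAE report due under both? |
|---|---|---|---|---|
| No | None | SAE | Neither AE nor SAE | No: rules differ |
| No | Non-serious | SAE | Non-serious AE (the symptom) | No: rules differ |
| No | Serious | SAE | SAE (the sequela) | Yes, though the reported term differs |
| Yes | None | SAE | Reported; seriousness not stated | Open |
| Yes | Non-serious | SAE | Reported; seriousness not stated | Open |
| Yes | Serious | SAE | SAE | Yes |

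**Result.** Of the 2 × 3 = 6 combinations, an SAE report is due under both rules in 2, the answer is open in 2, and the rules differ outright in 2. The two that differ form a single class: no self-harm intent and no serious sequelae. Appendix 3 draws its line at self-harm intent alone, so within that class it makes no difference whether the overage was accidental or deliberate.

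**Which row is realistic.** Study treatment is given in the clinical facility (Section 7.6), as one infusion by calibrated constant-rate pump (Section 5.1). A dosing or pump error is therefore the plausible route to an overage, which falls in the rows without self-harm intent. Opportunities are few: 2 groups × about 70 participants = about 140 infusions, plus any replacements. The documents give no overdose rate, and none is assumed here.

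**The case against.** The best defence is that Section 9.3 governs. It is expressly limited to this study and uses mandatory language. Appendix 3 is visibly a generic sponsor text: it mentions oncology protocols and endpoints of death, neither of which applies here, and its overdose sentence uses the softer *should* and concerns verbatim terms. A site could reasonably send every overage through the SAE route, and the error would then be on the side of over-reporting. This weakens the conflict but does not remove it. No text gives Section 9.3 precedence, and its own cross-reference leads to the contrary rule. The verbatim-term reading does not help either. Without symptoms there is no other term to report; with non-serious symptoms, Appendix 3 yields a non-serious AE where Section 9.3 still wants an SAE.

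It can also be said that little would be lost. Dispensing records (Appendix 2), the dosing listing (SAP Section 6.4) and documented deviations (SAP Section 6.2) would still show the overage, and Section 9 requires immediate safety concerns to be discussed with the sponsor. That stands, and it limits the severity.

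One supporting argument should not be pressed. Appendix 3 does bring other special cases into the SAE process: "Pregnancy and potential drug induced liver injury (DILI) must follow the same transmission timing and processes to BMS as used for SAEs". That overdose is missing from that sentence is only an argument from silence. The direct contradiction does not need it.

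A reader might infer several separate conflicts by splitting accidental from intentional overages. Appendix 3 does not make that split, so there is one conflict. A reader might also infer a distorted comparison of SAEs between treatments. The documents do not support that: both rules apply equally to both groups, and the SAP lists SAEs without a comparative SAE rate.

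**Conclusion.** The inconsistency is real and minor. For an abatacept overage without self-harm intent and without serious sequelae, Section 9.3 requires an SAE report and Appendix 3 does not. For a self-harm overdose without serious sequelae, Appendix 3 requires reporting but does not say that the event is serious, so its SAE label is unsettled as well.

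The size is one SAE record or none per such overage, over about 140 supervised infusions, with an unknown and probably low frequency. The consequences stay within the safety records: the SAE label, the 24-hour report, the SAE listing and any AE tabulation. The Cmax and AUC(INF) analyses, the biocomparability criterion and the power do not depend on how an overdose is labelled.

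The conclusion assumes that no precedence rule sits in redacted text or in site instructions outside the two documents.

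**What to change.** Keep Section 9.3 and amend Appendix 3. Let both the overdose sentence and the sentence barring non-AEs from being SAEs begin: *Except for overdose of study treatment as defined in Section 9.3, which for this study is reported through the SAE process within 24 hours,*. This removes the contradiction and also settles the self-harm case for abatacept. Overdoses of concomitant medication, which Section 9.3 does not cover, remain under Appendix 3 as now.

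The cost is small. Some symptom-free overages will be reported as SAEs. The change also needs IRB/IEC handling: Appendix 2 requires approval of an amendment before a change is implemented and notification for an administrative letter, and the documents do not show which would suffice here. Sites need a notice. No visit, procedure, participant or SAP text changes, since SAP Section 6.6.2 already lists whatever SAEs are reported.

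The alternative, deleting the mandatory rule in Section 9.3 and letting Appendix 3 decide seriousness, would also be consistent. It withdraws a study-specific safety requirement, however, and is a policy decision for the sponsor rather than a correction of wording.

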9.4 Safety

Planned time points for all safety assessments are listed in the Schedule of Activities.

9.4.1 Physical Examinations

Refer to Schedule of Activities.

9.4.1.1 Medical Photography

Initial and subsequent photographs may be taken of any areas of rash and/or of the IV injection site (for any local reaction such as redness, swelling, or rash) that may develop after the start of the infusion.

9.4.2 Vital signs

Refer to Schedule of Activities.

9.4.3 Electrocardiograms

Refer to Schedule of Activities.

9.4.4 Clinical Safety Laboratory Assessments

Investigators must document their review of each laboratory safety report.

A local laboratory will perform the analyses and will provide reference ranges for these tests.

Results of clinical laboratory tests performed on Day -1 must be available and reviewed prior to dosing.

Hematology	
Hemoglobin Hematocrit Total leukocyte count, including differential Platelet count	
Chemistry	
Aspartate aminotransferase (AST) Alanine aminotransferase (ALT) Total bilirubin Direct bilirubin Alkaline phosphatase Lactate dehydrogenase (LDH) Creatinine Blood Urea Nitrogen (BUN) Uric acid Fasting glucose	Total Protein Albumin Sodium Potassium Chloride Calcium Phosphorus Magnesium Creatine kinase (screening only)
Urinalysis	
Protein Glucose Blood Leukocyte esterase Specific gravity pH Microscopic examination of the sediment if blood, protein or leukocytes esterase are positive on the dipstick	
Serology	
Serum for hepatitis C antibody, hepatitis B surface antigen (HBsAg), hepatitis B core antigen antibody (anti-HBc), HIV-1 and -2 antibodies will be conducted (screening only)	
Other Analyses	
Urine test for drugs of abuse including cotinine (screening and Day -1) Urine or breath alcohol test (screening and Day -1)	
Thyroid-stimulating hormone (TSH) with reflex to free triiodothyronine (T3) and free thyroxine (T4) as applicable (screening only)	
QuantiFERON-TB Gold test (screening only)	
Pregnancy test (quantitative results) (WOCBP only): screening, on Day -1, Day 15, Day 29, Day 57, and Day 71 (study discharge).	
Follicle stimulating hormone (FSH) (screening only for women only)	

9.4.5 Suicidal Risk Monitoring

Not applicable.

9.4.6 Imaging Safety Assessment

Not applicable.

9.4.7 Chest X-ray

A posterior-anterior and lateral chest x-ray, performed during screening, is required for all participants. All participants must have a chest x-ray negative for TB to be entered in this study. The chest x-ray result will be recorded on the appropriate page of the CRF.

9.5 Pharmacokinetics

Pharmacokinetics of abatacept will be derived from serum concentration versus time data. The PK parameters to be assessed include:

C _{max}	Maximum observed serum concentration
T _{max}	Time of maximum observed serum concentration
AUC(0-28 day)	Area under the serum concentration-time curve from time zero to 28 days after dosing
AUC(0-T)	Area under the serum concentration-time curve from time zero to time of last quantifiable concentration
AUC(INF)	Area under the serum concentration-time curve from time zero extrapolated to infinite time
T-HALF	Terminal phase elimination half-life in serum
CLT	Clearance
V _{ss}	Volume of distribution at steady-state

Individual participant PK parameter values will be derived by non-compartmental methods by a validated PK analysis program. Actual times will be used for the analyses.

9.5.1 Pharmacokinetics: Blood Collection and Processing

Table 9.5.1-1 lists the sampling schedule to be followed for the assessment of PK. The capture of precise PK sampling times relative to the actual dosing time is integral to the PK analysis and must be accurately recorded on the eCRF. The date and time of sample collection must be recorded so that compliance with the sampling schedule can be confirmed.

Table 9.5.1-1: Pharmacokinetic Sampling Schedule for Abatacept

Study Day of Sample Collection	Event	Time (Relative To Start of Infusion of Abatacept) Hour: Min	Blood Sample for Serum Abatacept
1	predose	00:00	X
1		00:15	X
1	EOI ^a	00:30	X
1		01:00	X
1		02:00	X
1		06:00	X
1		12:00	X

Table 9.5.1-1: Pharmacokinetic Sampling Schedule for Abatacept

Study Day of Sample Collection	Event	Time (Relative To Start of Infusion of Abatacept) Hour: Min	Blood Sample for Serum Abatacept
2		24:00	X
4		72:00	X
8		168:00	X
15		336:00	X
22		504:00	X
29		672:00	X
43		1008:00	X
57		1344:00	X
71		1680:00	X

^a EOI=End of Infusion, This sample should be taken immediately prior to stopping the infusion (preferably within 2 minutes prior to the end of infusion). If the end of infusion is delayed to beyond the nominal infusion duration, the collection of this sample should also be delayed accordingly.

The serum samples will be analyzed for abatacept by a validated enzyme-linked immunosorbent assay (ELISA).

Detailed instructions for the PK blood collection, labeling, processing, storage, and shipping will be provided to the site in the procedure manual.

[REDACTED]

9.8.2 Immunogenicity Assessments

Table 9.8.2-1 lists the sampling schedule to be followed for immunogenicity assessments. Blood samples for determination of antibodies to abatacept and time-matched PK samples will be collected on Days 1, 15, 29, 57, and 71. Participants who seroconvert and continue to have a high titer at study discharge that is considered to be significantly increased versus baseline will be asked to return for follow-up assessment(s) for anti-abatacept antibodies approximately every 4 months until their titers and/or sero-status are judged to be stable by the investigator.

Table 9.8.2-1: Immunogenicity Sample Schedule

Study Day of Sample Collection	Event	Time (Relative To Start of Infusion of Abatacept Hour: Min)	Blood Sample for Immunogenicity
1	predose	00:00	X
15		336:00	X
29		672:00	X
57		1344:00	X
71		1680:00	X

A validated, sensitive, electrochemiluminescence assay (ECL) method will be used to detect anti-abatacept-antibodies with specificities to “CTLA4 and possibly Ig” and “Ig and/or Junction Region”.³⁴

Samples that are confirmed positive with specificity to “CTLA4 and possibly Ig” antibodies with the ECL immunogenicity assay will be further analyzed with a validated, in vitro, cell-based bioassay to determine whether the anti-abatacept-antibodies have neutralizing activity.

Record the date and time of sample collection so that compliance with the sampling schedule can be confirmed. Detailed instructions for the immunogenicity blood collection, labeling, processing, storage, and shipping will be provided to the site in the procedure manual.

9.9 Health Economics OR Medical Resource Utilization and Health Economics

Health Economics/Medical Resource Utilization and Health Economics parameters will not be evaluated in this study.

10 STATISTICAL CONSIDERATIONS

10.1 Sample Size Determination

Biocomparability of Treatment A to Treatment B will be concluded if the 90% CIs for the ratios of geometric means for abatacept C_{max} and AUC(INF) are contained within 80% to 125%. Seventy participants per treatment group (Treatment A or Treatment B) will provide 88% power to conclude that Treatment A is biocomparable to Treatment B if Treatment A increases abatacept exposure by 10% compared to Treatment B; if Treatment A decreases abatacept exposure by 10%, 70 participants per treatment group will provide 83% power to conclude that Treatment A is biocomparable to Treatment B.

Participants who drop out will be replaced to ensure that there will be at least 65 evaluable participants per treatment group. Sixty-five participants per treatment group will provide 86% power to conclude that Treatment A is biocomparable to Treatment B if Treatment A increases abatacept exposure by 10% compared to Treatment B and 80% power if Treatment A decreases abatacept exposure by 10%.

These calculations assume that AUC(INF), and Cmax are log-normally distributed with between-participant standard deviation of 0.21 for Cmax and 0.27 for AUC(INF), [REDACTED]

10.2 Populations for Analyses

For purposes of analysis, the following populations are defined:

Population	Description
All Enrolled Participants	All participants who sign informed consent
All Treated Participants	All participants who receive study treatment
Pharmacokinetic Population	All participants who receive abatacept and have any available concentration-time data.
Evaluable Pharmacokinetic Population	All participants in the PK Population with adequate PK profiles for accurate estimation of PK parameters. All available derived PK parameter values will be included in the PK data set and reported, but only participants with evaluable PK will be included in the summary statistics and statistical analysis.

All participants who receive study treatment will be included in the safety data set.

10.3 Statistical Analyses

The statistical analysis plan will be developed and finalized before database lock and will describe the selection of participants to be included in the analyses, and procedures for accounting for missing, unused, and spurious data.

A description of the participant population will be included in the statistical output reported, including subgroups of age, gender, and race.

No efficacy analyses will be performed.

Below is a summary of planned statistical analyses of the primary and secondary endpoints.

